### **4.4 Sample size calculation**

The primary outcome is the probability of amputations after 12 months. The meta-analysis showed a 15% difference (11% vs. 26%; Brouwer 2020) of amputations between patients treated with HBOT and patients treated conservatively. The sample size calculation is based on a one-sided type I error of 5% and a power of 90% to control for a type 2 error. A

generalization of the power requirements for testing multiple active treatments to one control group was used as proposed by Dunnett (Dunnett 1984).

The critical values for continuation of a treatment arm are odds ratios of 0.76 and 0.352, which are in accordance with a drop in amputations from 26% to 21% and to 11%. If the difference is <5% the HBOT treatment arm is deemed futile, while a difference of 15% or higher is deemed superior. Based on these critical values the required number of patients in each group in each stage is 68, leading to a required maximum number of 544 patients. The sample size calculation is based on a generalization of Whitehead and Jaki (Whitehead 2009, Jaki 2019). Taking into account a possible loss to follow-up of 5%, we will need a total of (up to) 573 patients.

This leads to the following stopping rules and possible scenarios after the interim analysis (using the chi-square test for differences in percentages between the groups) (see figure 2 below):

- 1) If one of the HBOT treatment groups leads to a significantly less than 5% improvement in amputation rate as compared to controls (based on the expected 26% vs 21% difference, i.e. an OR of 0.76), then this treatment group will be discontinued as it is futile.
- 2) IF a HBOT treatment group proves to decrease amputation rate significantly by >15% (26% vs 11%; OR: 0.352) as compared to controls, then superiority of a treatment arm is proven and the trial will be discontinued as it has reached its aim. If more than one HBOT-treatment arm shows this superiority, the group with the lowest number of HBOT treatments is deemed superior.
- 3) If the HBOT group(s) show(s) minor improvements in amputation rate (between 5% and 15%) over control, then these groups will continue in the second stage of the trial.

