#### 7.1.1 Main study parameter/endpoint

- Major amputation rate (above ankle) and (major) amputation-free survival after 12 months of follow-up

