#### 7.1.2 Secondary study parameters/endpoints (if applicable)

- Complete wound healing
- Time to reach complete wound healing
- Freedom from minor amputation (below ankle)
- Pain score (VAS)
- Health-related quality of life scores
  - EQ-5D-5L
  - SF-12
  - Vascuqol-6
- Costs related to HBOT and conventional therapy during follow-up period
- Patients' out of pocket expenses related to disease or treatment (travel expenses etc.)
- Mortality
- Patients' perception of improvement (through one anchor question)
- Forefoot TcpO2 before, during and after (HBOT) treatment (if equipment is available)

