## 9. STATISTICAL ANALYSIS

All analyses will be conducted according to the intention-to-treat principle. Baseline characteristics are summarized with descriptive statistics. Differences between dichotomous variables (like the amputation rate) will be expressed as a risk differences and Numbers Needed to Treat or Harm. Statistical precision will be expressed as 95% confidence intervals. Differences between continuous variable will be expressed as difference in means. If outcome parameters are unevenly distributed, they will be expressed as medians and inter-quartile ranges.

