### 9.2 Secondary and other study parameters

Differences in (semi-)continuous variables between the two treatment groups (such as the VAS, TcpO2 and quality of life scores) will be analysed with the Student t-test in case of normally distributed data and otherwise the non-parametric Mann-Whitney U test, after correcting for baseline differences, if any.

Time to complete wound healing will be estimated using Kaplan-Meier survival analysis and differences between the groups will be analysed using the log-rank test. Changes over time of TcpO2 and quality of life scores will be analysed using the Wilcoxon test. Potential confounding factors will be adjusted using Cox proportional hazards regression modelling.

The economic evaluation of additional HBOT will be performed as a cost-effectiveness analysis from a societal perspective. Additionally, a cost-utility analysis will be performed with the costs per quality adjusted life-year (QALY) as outcome. As the time horizon is restricted to 12 months, no discounting (of costs and effects) will be performed.

The EQ-5D is used to generate health status scoring profiles over time, which will subsequently be translated in QALYs by applying time trade-off based health utility algorithms and assuming that interpolation between successive measurements best reflects a patient's health status during the year. Sensitivity analyses will be performed to account for sampling variability, for plausible ranges in unit costs, and for different health

utility algorithms. In addition, a budget impact analysis will be undertaken to assess the possible cost savings of HBOT if applied to all eligible patients on a national scale.

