### **9.3 Interim analysis**

After inclusion of 68 patients in each group and three months of follow-up, an interim analysis will be conducted (see figures 1 and 2). From our previous trial (Santema 2018) we know that the vast majority of amputations occurs within three months of follow-up. Whether and how the trial will continue will depend on the outcome of the interim analysis, which is the main feature of the MAMS study design. This is described in chapter 4.4.

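### The between-arm test of forefoot TcpO2 at 3 and 12 months can use only living patients who kept the foot, so it is not intention-to-treat and is probably tilted against HBOT

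*Protocol*

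**What the plan says.** Section 7.1.2 lists forefoot TcpO2 as a secondary endpoint, taken "before, during and after (HBOT) treatment (if equipment is available"). Table 1 in section 7.3 schedules it before randomisation, at 3 months and at 1 year.

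The first sentence of section 9.2 covers the comparison between groups. TcpO2, among other continuous outcomes, "will be analysed with the Student t-test in case of normally distributed data and otherwise the non-parametric Mann-Whitney U test", and this is done "after correcting for baseline differences, if any". A later sentence covers change: "Changes over time of TcpO 2 and quality of life scores will be analysed using the Wilcoxon test". It does not say whether that test is paired within an arm or compares arms.

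Section 9 opens with a general rule: "All analyses will be conducted according to the intention-to-treat principle". The main endpoint in section 7.1.1 is "Major amputation rate (above ankle) and (major) amputation-free survival after 12 months of follow-up". Section 4.4 designs the trial on "26% vs 11%; OR: 0.352", and section 9.3 says that "the vast majority of amputations occurs within three months of follow-up".

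The protocol does not state how a patient who has lost the leg or died enters the TcpO2 analysis.

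**The concern.** After a major amputation there is no forefoot on that leg. The value is undefined rather than missing, and the same holds after death. The tests named in section 9.2 need a value for each patient, so as written they drop these patients. If HBOT does what the trial hopes, more patients are dropped from control than from HBOT.

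If the limbs lost tend to be the poorly oxygenated ones, control loses more of its low values. Limbs that HBOT saves stay in the HBOT average and pull it down. A real limb-salvage benefit could then be reported next to a null or adverse oxygenation result, and the two would appear to conflict when the second is only a product of selection.

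**Working it through.** **Design figures.** Odds ratio: (0.11/0.89)/(0.26/0.74) = 0.352, as section 4.4 states. Maximum size: 68 × 4 arms × 2 stages = 544, and 544/0.95 = 573 after rounding up, also as stated. The protocol gives no design figure for TcpO2.

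**Inputs from the protocol.** Major amputation p = 0.26 (control) and 0.11 (HBOT); 68 per arm per stage, so 136 in an arm that completes both stages. The rates are for 12 months. Applying them at 3 months rests on the statement in section 9.3 about early amputation and slightly overstates the loss at that visit.

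**Assumptions.** TcpO2 is roughly normal and HBOT has no effect on it. Its correlation with the latent tendency to keep the limb is ρ. The protocol gives no ρ, so a range is shown.

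**Patients with a readable foot.** At 136 per arm: 136 × 0.74 = 101 control and 136 × 0.89 = 121 HBOT. At 68 per arm: 50 and 61. This is before deaths, forefoot amputations and missing equipment.

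**Shift in the mean among limbs kept.** In SD units the shift is ρ·h, with h = φ(z_p)/(1−p).
- Control: z = −0.643, h = 0.3244/0.74 = 0.438.
- HBOT: z = −1.227, h = 0.1880/0.89 = 0.211.
- HBOT minus control: −0.227·ρ.

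**Chance of a significant result against HBOT.** The variance among limbs kept is 1 − ρ²·h(h − z). At ρ = 0.5 this is 0.881 (control) and 0.924 (HBOT). With 136 per arm, SE = √(0.881/100.6 + 0.924/121.0) = 0.128. The chance is then Φ(−1.96 + 0.1135/0.128) = Φ(−1.07) = 0.14. Over the range (nominal 2.5% on this side):

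| ρ | Bias, SD | 68 per arm | 136 per arm |
|---|---|---|---|
| 0 | 0 | 2.5% | 2.5% |
| 0.25 | −0.06 | 5% | 6% |
| 0.5 | −0.11 | 9% | 14% |
| 0.75 | −0.17 | 17% | 30% |
| 1 (bound) | −0.23 | 33% | 58% |

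**With baseline correction (simulation).** At ρ = 0.5 for both readings, the bias of −0.11 SD falls to −0.06 SD if baseline and follow-up TcpO2 correlate 0.5, and to −0.04 SD if they correlate 0.7. If limb loss is tied more to baseline (0.5) than to follow-up TcpO2 (0.25), the adjusted bias is 0 to +0.03 SD.

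**Within-patient change (same simulation).** When limb loss relates equally to both readings, there is no difference between arms. When it relates more to baseline, the mean change is −0.11 SD in control and −0.05 SD in HBOT, which favours HBOT.

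**Ranking death and amputation below all readings.** With no oxygenation effect and ρ between 0 and 0.5, a Mann-Whitney test on such ranks is significant for HBOT in about 19–34% of trials at 68 per arm and 33–58% at 136, through amputation alone.

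**The case against.** A reader might infer that all three tests are biased against HBOT. The documents do not support this. The Wilcoxon sentence concerns change over time and may mean a paired test within each arm, which compares no arms. Selection bias in change can be nil or can favour HBOT.

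Nor is the direction certain for the between-arm test. It requires that lost limbs have lower TcpO2 than kept ones. The protocol makes this plausible: low TcpO2 is one of its criteria for ischaemia (section 4.2), and section 12.1(i) says forefoot TcpO2 could help to predict treatment success. The same item says no biomarker predicts the effect of HBOT, and no correlation or SD is given. The 0.23 SD bound needs perfect correlation.

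The stated baseline correction shrinks the bias and has to be counted. But it is conditional on baseline differences being present and no method is named. Randomised arms should be similar at baseline, so it may not be applied. It is not a dependable safeguard.

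It can also be said that intention-to-treat means analysis as allocated, and that the handling of amputation and death belongs in a statistical analysis plan. That is fair for the handling rule, which a later plan could supply. It does not remove the tension in the protocol, which names the tests, applies intention-to-treat to every analysis, and includes an endpoint that a quarter of controls are expected to be unable to provide.

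Finally, a composite rank test is sometimes seen as the cure. It includes all patients, but it brings the primary endpoint into a physiological measure and can be significant with no oxygenation effect. It answers a different question.

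**Conclusion.** The point holds for the between-group t-test or Mann-Whitney. At the design rates, 15 percentage points more HBOT than control patients (89% against 74%) keep a readable foot, so the comparison is not of the randomised groups. It is likely, though not certainly, tilted against HBOT: roughly 0.06–0.17 SD unadjusted for ρ of 0.25–0.75, and at ρ = 0.5 about 0.04–0.06 SD if baseline is adjusted for. These sizes rest on normality, on the assumed ρ and on the 26% and 11% rates. The false-signal rates also assume a TcpO2 reading for every limb kept. Missing equipment would lower them by shrinking the sample, but would not remove the bias.

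The Wilcoxon analysis of change shares the restriction to limb-intact survivors, but no direction of bias can be claimed for it. Someone might also infer a threat to the main result. There is none: amputation and amputation-free survival do not depend on TcpO2, which is a secondary endpoint.

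**What to change.** In section 9.2:

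- State that TcpO2 at 3 and 12 months, and its change from baseline, will be reported in limb-intact survivors as descriptive results, with no between-arm efficacy claim.
- Show by arm and visit the numbers with a reading, with major amputation of the target leg, dead, and without equipment.
- If a test on all randomised patients at sites with equipment is wanted, add as supportive a ranking with death lowest, major amputation next, then measured TcpO2. Label it as a composite of limb loss and oxygenation, not as an effect on TcpO2.

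Amputation and mortality are already recorded under section 7.3, so the outcome data need no addition; equipment availability only has to be tabulated. The cost is that this secondary endpoint yields no confirmatory difference in mmHg.

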### **9.3 Interim analysis**

After inclusion of 68 patients in each group and three months of follow-up, an interim analysis will be conducted (see figures 1 and 2). From our previous trial (Santema 2018) we know that the vast majority of amputations occurs within three months of follow-up. Whether and how the trial will continue will depend on the outcome of the interim analysis, which is the main feature of the MAMS study design. This is described in chapter 4.4.

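### The interim applies limits set on 12-month amputation rates after only three months of follow-up, and a crossing then counts as proven superiority although both main endpoints are defined at 12 months

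*Protocol*

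**What the plan says.** Section 4.4 fixes the time point of the outcome that drives the design: "The primary outcome is the probability of amputations after 12 months". The critical values are odds ratios of 0.76 and 0.352, described as "in accordance with a drop in amputations from 26% to 21% and to 11" percent. In points, an arm is futile below 5 and superior at 15 or more. The numbered rules in the same section add a significance requirement to both limits. When the upper limit is crossed, rule 2 states that "superiority of a treatment arm is proven and the trial will be discontinued as it has reached its aim".

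Section 7.1.1 gives the main endpoints: "Major amputation rate (above ankle) and (major) amputation-free survival after 12 months of follow-up".

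Section 9.3 sets the interim: "After inclusion of 68 patients in each group and three months of follow-up, an interim analysis will be conducted". It refers to section 4.4 for the consequences and does not restate the limits. Its reason for three months is that, in the sponsor's previous trial, by far most amputations had occurred by then. It gives no figure for that share and does not say whether major amputations alone are meant. Section 7.7 repeats that the study may end early for superiority.

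**The concern.** Limits and data refer to different time points. A 15-point limit taken from 12-month rates has no stated meaning for a three-month difference, because the protocol does not say what three-month difference corresponds to the planned 12-month effect.

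The superiority rule matters most. It ends the trial and calls the question settled while the last-recruited patients have three months of data and the named primary endpoint is incomplete. If HBOT delays some amputations rather than preventing them, the difference at three months exceeds the one at 12 months, and the trial would publish the larger one. Section 4.4 does not say that randomised patients complete 12 months after such a stop, nor that the conclusion waits for their data.

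The futility rule has the same mismatch. If the difference is still building up at three months, a 5-point limit is stricter than it would be at 12 months. An arm closed at the interim takes no further patients, so the decision is hard to undo.

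**Working it through.** **1. The plan's own figures.**
- Odds ratios: (0.21/0.79)/(0.26/0.74) = 0.757 and (0.11/0.89)/(0.26/0.74) = 0.352. Both agree with section 4.4.
- Maximum size: 68 × 4 arms × 2 stages = 544, and 544/0.95 = 573. Both agree.
- The 68 per arm per stage can be reached with some boundary and variance choices, but section 4.4 names no boundary. It is taken as given.

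The limits therefore rest on 26%, 21% and 11%, which section 4.4 ties to 12 months.

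**2. Method.** With 68 per arm, let X (control) and Y (HBOT) be independent binomial counts with rates p_C and p_T. Five points is 0.05 × 68 = 3.4 patients, so an observed difference below 5 points means X − Y ≤ 3. Fifteen points is 0.15 × 68 = 10.2, so at least 15 points means X − Y ≥ 11. Each probability is the sum of Bin(x; 68, p_C) × Bin(y; 68, p_T) over the pairs that qualify.

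**3. Superiority when an early difference narrows.** The rates are assumed, because the protocol gives none at three months.

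| Data used | Control | HBOT | P(observed difference ≥ 15 points) |
|---|---|---|---|
| 3 months | 23% | 8% | 47% |
| 12 months | 26% | 16% | 22% |

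Rule 2 can also be read as requiring a difference significantly above 15 points. Taking this as (d − 0.15)/SE > 1.645, with d the observed difference and SE its unpooled standard error, the two chances are 5.1% and 1.0%. Crossings are then rare, but the order is the same.

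**4. Futility for an arm with true 12-month rates of 26% against 11%.** Suppose that a share f of the 12-month amputations has occurred by three months in both arms, and that every patient is counted at exactly three months. The interim rates are then 26f% and 11f%, and the expected difference is 15f points. The odds-ratio column uses raw counts.

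| f | Expected difference (points) | P(dropped), plain 5-point limit | P(dropped), OR above 0.76 | P(dropped), significantly below 5 points |
|---|---|---|---|---|
| 1 | 15.0 | 6.5% | 4.3% | 0.1% |
| 0.9 | 13.5 | 9.1% | 5.5% | 0.2% |
| 0.8 | 12.0 | 12.6% | 7.0% | 0.3% |

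Adding 0.5 to each cell of the odds ratio gives 4.7%, 6.0% and 7.7% in place of 4.3%, 5.5% and 7.0%.

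**5. Two variations on the plain 5-point limit.**
- All accrued follow-up is counted. Assume uniform recruitment, 80% of amputations by month 3 and a linear build-up to month 12. Stage-one recruitment over 12 months gives an average share of about 0.93 and a drop risk of 8.4%. Over 24 months the figures are about 0.96 and 7.4%.
- The benefit is all early (21% against 6% at three months, 26% against 11% at 12). The drop risk is 4.0%, below the 6.5% on 12-month data.

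**6. What rescaling the futility limit would do.** At f = 0.9 the limit becomes 4.5 points, or 3.06 patients. That still means X − Y ≤ 3, so the same arms are dropped. At f = 0.8 it becomes 4 points, or 2.72 patients, so X − Y ≤ 2 and the drop risk falls from 12.6% to 8.1%.

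**The case against.** The protocol does give a reason for three months. If nearly all amputations occur by then, the early and late differences are close, and an early look lets the design stop recruiting to poor arms. That is a fair ground for an early look. It does not supply the missing share, and it does not make a three-month result a 12-month one. The remark also comes from a trial that, according to section 1, included relatively superficial ulcers, whereas section 4.2 enrols Meggitt-Wagner stages 3 and 4.

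A reader might infer that effective arms will be dropped too often. The documents do not support this as a general statement. It needs the plain 5-point limit, the same share f in both arms, and counting stopped at exactly three months. Section 4.4 also states the futility limit as an odds ratio and as a significance rule, and section 9.3 does not say that later amputations are ignored. The rise is smaller on the odds-ratio reading, negligible on the significance reading, and reversed if the benefit comes early. The protocol also states no planned drop probability to compare with.

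A reader might likewise infer that the three-month look inflates false superiority claims. Under proportional shrinkage it does the opposite. With no true effect, the chance that any of three arms shows at least 15 points falls from 4.9% (f = 1) to 4.1% (f = 0.9) or 3.3% (f = 0.8). The objection to rule 2 is that it draws its conclusion on an endpoint not named as primary, and that an early difference may not last.

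**Conclusion.** The mismatch stands on the text alone: limits derived at 12 months are used unchanged at three, and rule 2 turns a crossing into a final claim before the primary endpoint is complete. No other section repairs this, and it should be corrected before the interim.

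The 47% against 22% shows what can happen if a difference narrows. It rests on assumed rates and on the observed-difference reading of the 15-point limit, and it is not a forecast. The futility effect is secondary and conditional: about 3 to 6 extra percentage points of drop risk per arm for f of 0.9 to 0.8 in the least favourable of the three readings, and less, none or the reverse otherwise. Its true size cannot be fixed without the three-month share and a single form of the rule.

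**What to change.** 1. In rule 2 of section 4.4, replace the statement that "superiority of a treatment arm is proven and the trial will be discontinued as it has reached its aim" with the following: a crossing at the interim may close recruitment, all randomised patients complete the planned 12-month follow-up, and superiority is claimed only on the 12-month primary endpoint.
2. In section 9.3, define the interim endpoint as major amputation within three months of randomisation, and give the share of 12-month amputations seen by three months in the sponsor's previous trial.
3. Settle which form of the futility rule applies (plain difference, odds ratio or significance), set that limit for three months, and recompute the error rate and power with it. If the share is near 90% and the plain difference is kept, rescaling changes no decision at 68 per arm.

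The cost is one protocol amendment and a rerun of the design calculation. The drawback is that a superiority claim waits up to nine months (12 − 3), for follow-up that sections 3 and 7.3 already plan.

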## **10. ETHICAL CONSIDERATIONS**

### **10.1 Regulation statement**

The DIONYSIUS trial will be conducted according to the principles of the Declaration of Helsinki (version of Seoul, 2008) and in accordance with the Medical Research Involving Human Subjects Act (WMO) and other guidelines, regulations and Acts.

### **10.2 Recruitment and consent**

Patients will be recruited by their vascular surgeon in one of the participating hospitals and will be informed both verbally and through the patient information form (attachment E1). They will be asked for written informed consent (attachment E2) by a local investigator, or a co-worker in the contributing center who is not the vascular surgeon of the patient, in accordance with the guidelines of the medical ethics review board.

